## 5.5 Multiple comparison and multiplicity

No adjustment for multiplicity will be applied to any endpoints, thus any inferential statistics will be nominal.

293 Version: 1.0 Status: Approved Approved Date: PTK0796-AP-17202 Statistical Analysis Plan

Omadacycline (PTK 0796)

Paratek Pharma, LLC

PTK0796-AP-17202 Statistical Analysis Plan

# **6 POPULATION SUMMARIES**

Unless otherwise stated, listings corresponding to all summaries in this section will be provided for all randomized subjects (ITT analysis population).

## 6.1 Subject Disposition

The number of subjects included in each of the analysis populations defined in this SAP and the reasons for exclusion will be summarized by treatment group. A listing will be provided to indicate each subject's inclusion/exclusion from the populations, and the reason for exclusion from a population will be presented.

A list of randomized subjects who did not meet all inclusion/exclusion criteria, and which criteria were not met will be presented.

The number and percentage of subjects completing the study (completing the EOT, PTE and FFU visits, as reported on CRF), as well as the completion status of EOT, PTE, and FFU visits will be presented. Reasons for not completing the study and for missing visits, as recorded on the eCRF, will be summarized (number and percentage) by treatment group for ITT, micro-ITT, CE and PTE populations.

The number and percentage of subjects completing and prematurely discontinuing test article and the reasons for discontinuation will be presented by treatment group. A listing of all subjects who prematurely discontinued from test article or who did not complete the study will be presented, along with the primary reason for discontinuation of test article or not completing the study.

The number of screen failures and reason for screen failure will be presented overall. For randomized subjects, a listing will be provided that indicates the date and time of randomization, randomization number, randomized treatment assignment, drug unit identifications, and corresponding drug codes.

## 6.2 Demographic and Baseline Characteristics

Demographic characteristics will be summarized in ITT, micro-ITT, CE-PTE, and ME-PTE populations analysis sets defined in this SAP. The summary table will include age, race, and ethnicity, along with baseline characteristics for height, weight, body mass index (BMI), number of prior urinary tract infections (UTIs) (lifetime), and renal function. Age will be summarized as a continuous variable and as categorical, based on the following groups: 18 to 45 years, > 45 to 65 years.

Renal function will be categorized as normal (creatinine clearance [CrCl] > 89 mL/min), mild renal impairment (CrCl > 60 to 89 mL/min), moderate renal impairment (CrCl 30 to 60 mL/min) and severe renal impairment (CrCl < 30 mL/min). Creatinine clearance will be calculated from the local laboratory data and will be determined from the Cockcroft-Gault equation, for female subjects:

93 Version: 1.0 Status: Approved Approved Date: PTK0796-AP-17202 Statistical Analysis Plan

Omadacycline (PTK 0796)

Paratek Pharma, LLC

PTK0796-AP-17202 Statistical Analysis Plan

$$CrCl = \frac{(140 - \text{age [yrs]}) * \text{weight [kg]} * (0.85)}{Cr [mg/dL] * 72}$$

Gender will not be included in the summary, as all subjects enrolled in this study will be female, per inclusion criteria.

General medical history will be coded using Medical Dictionary for Regulatory Activities (MedDRA) and summarized by system organ class (SOC) and preferred term (PT).

Results of the Modified Patient Symptom Assessment Questionnaire (mPSAQ) will be summarized as the number and percentage of subjects responding to each item, including individual severity symptom scores, individual bothersome scores, and overall severity and bothersome score.

#### 6.3 **Baseline Microbiology**

#### 6.3.1 Urine

The microbiological assessment of the urine culture by the local laboratory will be summarized by treatment group for the ITT and micro-ITT populations.

The number of subjects with local urine culture performed, number of subjects with a clean catch sample, number of subjects with urine culture growth and number of isolates per subject where CFU count  $\geq 10^5$  CFU/mL.

Each isolate identified will also be reported and will include the CFU counts as recorded on the CRF ( $<10^3$  CFU/mL,  $10^3 \le$  and  $<10^4$  CFU/mL,  $10^4 \le$  and  $<10^5$  CFU/mL, and  $\ge 10^5$  CFU/mL).

Test article received disk diffusion value (mm) to baseline pathogen will be provided for micro-ITT population.

All of the below reports will be provided for micro-ITT and ME populations.

- The number and percentage of subjects with a positive urine culture by pathogenic organism will be provided for the micro-ITT and ME populations.
- The number and percentage of subjects with a Gram-positive organism (aerobes and anaerobes) and with a Gram-negative organism (aerobes and anaerobes) will be presented by genus and species.
- The number and percentage for minimum inhibitory concentration (MIC) data will be provided as:
  - o The MIC distribution to omadacycline and levofloxacin, across treatment groups
  - The MIC distribution to the test article received, by treatment group
  - MIC summary statistics (ie, range, MIC50, and MIC90) to the test article received. The MIC range will be provided for all baseline pathogens. The MIC50 and MIC90 will be

Number: GEN-STP-0293 Version: 1.0 Status: Approved Approved Date: PTK0796-AP-17202 Statistical Analysis Plan

Omadacycline (PTK 0796)

#### PTK0796-AP-17202 Statistical Analysis Plan

provided only for those pathogens isolated at least 10 times in a treatment group.  $MIC_{50}$  and  $MIC_{90}$  values are defined as the lowest concentration of the antibiotic at which 50% and 90% of the isolates were inhibited.

• MIC summary statistics (ie, range, MIC50, and MIC90) to the test article received for each pathogen at baseline.

A listing will be provided that includes for each subject all baseline and post-baseline isolates identified by Genus and species from the local and central urine culture including the CFU count and whether or not the isolate is a pathogen.

#### 6.3.2 Blood

Blood culture samples are taken at screening and as required during treatment. If bacteria are isolated from baseline blood cultures, repeated blood cultures will be collected. If subsequent blood cultures were also positive, repeated blood cultures as necessary were taken until negative blood cultures were obtained.

The pathogenic organisms identified from the baseline blood culture will be presented by genus and species.

The number and percentage of subjects with a positive blood culture by pathogenic organism will be provided for the micro-ITT and ME populations. The number and percentage of subjects with a Gram-positive organism (aerobes and anaerobes) and with a Gram-negative organism (aerobes and anaerobes) will be presented by genus and species.

A listing will be provided that includes all baseline and post-baseline isolates obtained from the blood.

Similar tables providing the MIC data for the pathogens identified from the baseline blood cultures will be provided for the micro-ITT and ME populations as described for the urine cultures in Section 6.3.1 above.

#### 6.4 General Medical History, AP, and UTI History

Significant medical history (at any time) and any medical history within the past 6 months including ongoing medical conditions at the time of signing of the informed consent form (ICF) will be recorded.

In addition, subject history of prior UTI infection and AP will be captured, where possible, diagnoses are to be recorded. Of note, any event or change in the subject's condition or health status occurring after signing the ICF will be reported as an AE. All medical history will be coded using the MedDRA.

The incidence of medical history abnormalities will be summarized using descriptive statistics by SOC and PT. Patients are counted only once in each PT and SOC category. Summaries will be presented by treatment group and for all patients.

93 Version: 1.0 Status: Approved Approved Date: PTK0796-AP-17202 Statistical Analysis Plan

Omadacycline (PTK 0796)

Paratek Pharma, LLC

PTK0796-AP-17202 Statistical Analysis Plan

### 6.5 **Prior Medications**

Treatments that have been administered within the 7 days prior to the date of informed consent, or during the Screening phase, will be recorded in the eCRF. The investigator is to instruct the subject to notify the study site about any new medications he/she takes after the start of the test article. All medications and significant non-drug therapies (including physical therapy and blood transfusions) administered after the subject starts treatment with test article must be listed in the eCRF (see Section 9). In addition, for antibacterial agents and anti-emetics administered, the dose, unit, frequency and route must be entered in the eCRF.

If a medication is taken prior to the first dose of test article or if their start date is unknown, then it will be summarized as a prior medication. Medications are considered concomitant if taken on or after the first dose of test article, or if their stop date is unknown or marked as continuing. Thus, in cases where a medication starts prior to the first dose, and continues throughout the treatment period, the medication will be summarized as both prior and concomitant.

Summary of prior antiemetic medication will also be provided for the ITT population.

Summarized for ITT and micro-ITT populations.

#### 6.6 **Protocol Deviations**

Deviations will be reviewed in a blinded manner by the sponsor and categorized into general categories (eg. inclusion/exclusion criteria). The sponsor will also categorize the protocol deviations as major and minor. Review of deviations will be conducted and finalized prior to unblinding the database.

A major deviation is defined as one that potentially affects the efficacy and/or safety analyses.

The number and percentage of subjects with at least one major protocol deviation or with at least one minor protocol deviation will be summarized for the ITT and micro-ITT population. The summaries of major deviations will also be presented by category.

A listing of all protocol deviations will be provided.

#### 6.7 Other Baseline Summaries

Abnormal laboratory results and abnormal vital signs at baseline will be reported.

At Screening, a full physical examination will include the examination of general appearance, skin, neck (including thyroid), eyes, ears, nose, throat, lungs, heart, abdomen, back, lymph nodes, extremities, and vascular and neurological systems. If indicated based on medical history and/or symptoms, rectal, external genitalia, breast, and/or pelvic exams may be performed.

Significant and relevant findings that are present prior to the start of test article must be included in the subject's eCRF. Relevant findings (except for signs and symptoms related to the index AP) that are present prior to the start of test article must be included in the relevant medical

93 Version: 1.0 Status: Approved Approved Date: PTK0796-AP-17202 Statistical Analysis Plan

Omadacycline (PTK 0796)

Paratek Pharma, LLC

PTK0796-AP-17202 Statistical Analysis Plan

history/current medical conditions screen on the subject's eCRF. Significant findings made after the start of test article which meet the definition of an AE must be recorded on the AE screen of the subject's eCRF.

Subject listings of all physical examination results by body system will be provided.

93 Version: 1.0 Status: Approved Approved Date: PTK0796-AP-17202 Statistical Analysis Plan

Omadacycline (PTK 0796)

PTK0796-AP-17202 Statistical Analysis Plan

# 7 EFFICACY ENDPOINTS AND ANALYSES

## 7.1 Efficacy Endpoints

In this phase 2 study all efficacy endpoints are exploratory and are analyzed as per Table 4 below.

## Table 4Efficacy Endpoints

	Visit	Population
(Overall) Investigator's assessment of clinical response	PTE/EOT/FFU	ITT
		micro-ITT
		CE, ME
(Overall) Microbiologic response	PTE/EOT	micro-ITT
		ME
Modified Patient Symptom Assessment Questionnaire (mPSAQ)	By visit/day	ITT, micro-ITT, CE-EOT, CE- PTE

## 7.1.1 Investigator's assessment of clinical response

## 7.1.1.1 Investigator's Assessment of Clinical Response at EOT

The investigator will determine whether or not the subject meets the criteria of 1 of the following clinical outcomes:

- **Clinical Success**: The complete resolution or significant improvement of the baseline signs and symptoms of AP at the EOT visit such that no additional antimicrobial therapy is required for the current infection.
- **Clinical Failure:** No apparent response to therapy or persistence of signs and symptoms of infection at the EOT visit such that use of alternative or additional systemic antimicrobial therapy for the current infection is required or death prior to the EOT visit.
- **Indeterminate:** EOT visit not completed.

93 Version: 1.0 Status: Approved Approved Date: PTK0796-AP-17202 Statistical Analysis Plan

Omadacycline (PTK 0796)

PTK0796-AP-17202 Statistical Analysis Plan

#### 7.1.1.2 Investigator's Assessment of Clinical Response at PTE

For subjects who were determined to be a clinical success or indeterminate at the EOT visit, the investigator will determine whether or not the subject meets the criteria of 1 of the following clinical outcomes:

- **Clinical Success**: The complete resolution or significant improvement of the baseline signs and symptoms of AP symptoms at the PTE such that no additional antimicrobial therapy is required for the current infection.
- **Clinical Failure**: No apparent response to therapy or persistence of signs and symptoms of infection or reappearance of signs and symptoms at or before the PTE visit such that use of additional systemic antimicrobial therapy for the current infection is required, or death occurred at or before the PTE visit.
- Indeterminate: PTE visit not completed.

Overall Clinical Response at PTE (based on the investigator's assessment) is determined as follows (Table 5) from the investigator's assessments at the EOT and PTE Visits:

EOT Visit	PTE Visit	Overall Clinical Response at PTE Visit
Success	Success	Success
Success	Failure	Failure
Success	Indeterminate	Indeterminate
Failure	Success	Failure
Failure	Failure	Failure
Failure	Indeterminate	Failure
Indeterminate	Success	Indeterminate
Indeterminate	Failure	Failure
Indeterminate	Indeterminate	Indeterminate

 Table 5
 Investigator's Assessment of Clinical Response at PTE Visit

EOT = end of treatment; PTE = post-therapy evaluation.

The derived Overall Investigator's Clinical Response is based on the "worst case scenario" to accommodate for missing visit assessment and intercurrent events (eg rescue medication at EOT visit). For the ITT and micro-ITT populations, the proportion of subjects with a Clinical Success is defined using the following formula (missing information at the PTE visit will be counted as Indeterminate):

# of subjects with Clinical Success

(# of subjects with Clinical Success + # of subjects with Clinical Failure + # of subjects with Indeterminate response)

93 Version: 1.0 Status: Approved Approved Date: PTK0796-AP-17202 Statistical Analysis Plan

Omadacycline (PTK 0796)

Paratek Pharma, LLC

PTK0796-AP-17202 Statistical Analysis Plan

By definition, subjects in the CE-PTE population cannot have an Indeterminate response. Thus, for the CE population, the proportion of subjects with a Clinical Success is defined using the following formula:

# of subjects with Clinical Success

(# of subjects with Clinical Success + # of subjects with Clinical Failure)

#### 7.1.1.3 Investigator's Assessment of Clinical Response at FFU

For subjects that were determined to be a clinical success at the PTE visit, the investigator will determine whether or not the subject meets the criteria of 1 of the following clinical outcomes:

- **Clinical Cure:** The complete resolution or significant improvement of the baseline signs and symptoms of AP at FFU visit such that no additional antimicrobial therapy is required for the current infection.
- **Relapse:** The reappearance of signs and symptoms at or before the FFU Visit such that use of alternative or additional systemic antimicrobial therapy for the current infection.
- **Clinical Failure:** Death between the PTE and Final Follow-up or failure at PTE visit.
- **Indeterminate:** Final Follow-up visit not completed. If FFU visit assessment is not within the visit window the EOT response is defined as indeterminate.

Overall Response (based on the investigator's assessment) is determined as defined in Table 6.

Status: Approved Approved Date: Version: 1.0 PTK0796-AP-17202 Statistical Analysis Plan

Omadacycline (PTK 0796)

Paratek Pharma, LLC

PTK0796-AP-17202 Statistical Analysis Plan

Overall Clinical Response at PTE Visit	Clinical Response at FFU Visit	Overall Clinical Response at FFU Visit	
Success	Clinical Cure	Clinical Success	
Success	Clinical Failure	Clinical Failure	
Success	Indeterminate	Indeterminate	
Success	Relapse	Relapse	
Failure	Clinical Cure	Clinical Failure	
Failure	Clinical Failure	Clinical Failure	
Failure	Indeterminate	Clinical Failure	
Failure	Relapse	Clinical Failure	
Indeterminate	Clinical Cure	Indeterminate	
Indeterminate	Clinical Failure	Clinical Failure	
Indeterminate	Indeterminate	Indeterminate	
Indeterminate	Relapse	Relapse	

#### Investigator's Assessment of Clinical Response at FFU Visit Table 6

PTE = post-therapy evaluation; FFU = Final Follow-up

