#### **8.8.1.3 Investigator's Assessment of Clinical Response at Final Follow-up**

For subjects that were determined to be a clinical success at the PTE visit, the investigator will determine whether or not the subject meets the criteria of 1 of the following clinical outcomes:

- **Clinical Cure:** The complete resolution or significant improvement of the baseline signs and symptoms of AP at FFU visit such that no additional antimicrobial therapy is required for the current infection.
- **Relapse:** The reappearance of signs and symptoms at or before the FFU Visit such that use of alternative or additional systemic antimicrobial therapy for the current infection.
- **Clinical Failure:** Death between the PTE and Final Follow-up.
- **Indeterminate:** Final Follow-up visit not completed.

Omadacycline  
PTK0796-AP-17202-Version 1.0; 26Mar2018

Paratek Pharma, LLC.  
IND # 75,928 IND # 73,431

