# 4.4 Clinically Evaluable Population

The clinically evaluable (CE) population will consist of all ITT subjects who received test article, have acute uncomplicated pyelonephritis (AP), an assessment of outcome, and meet all other evaluability criteria.

Inclusion into the CE populations will be determined programmatically based on the data on the eCRF and a manual review by the Sponsor as necessary prior to unblinding. Details on allocation to each CE population are described in the Pathogen and CE.

Since patient count may differ depending on timepoint, CE populations will be defined by milestone visit (CE-EOT, CE-PTE and CE-FFU). To be included in the populations, subjects must meet all criteria defined below:

1. Qualifying infection:

Inclusion Criterion #2: Females age 18 years or older

93 Version: 1.0 Status: Approved Approved Date: PTK0796-AP-17202 Statistical Analysis Plan

Omadacycline (PTK 0796)

Paratek Pharma, LLC

PTK0796-AP-17202 Statistical Analysis Plan

Inclusion Criterion #3: Clinical signs and symptoms of acute uncomplicated pyelonephritis with onset or worsening within 96 hours prior to randomization.

Inclusion Criterion #4: A clean-catch midstream urine sample with dipstick analysis positive (at least ++) for leukocyte esterase or pyuria (white blood cell [WBC] count >  $10/\mu$ L in unspun urine or  $\ge 10$  per high power field in spun urine sediment).

2. Assessment of Outcome for CE population:

Subjects must meet all of the following to be included in the CE populations:

- Subject did not meet one of the exclusion criteria 6 through 15 of the protocol (Baseline event exclusion)
- Received the randomized test article and was at least 80% compliant with the dosing regimen (Compliance to test article intake).
- Study personnel involved in the assessment of efficacy remained blinded to study treatment, unless a treatment limiting AE occurred which required emergency unblinding. In addition, for each endpoint the following needs to be satisfied, as appropriate:
  - a. For the CE-EOT population:
    - i. Completed the investigator's assessment of clinical response (i.e., was not deemed an indeterminate outcome) at the EOT visit, and
    - ii. The EOT visit occurred on the day of, or within  $\pm 2$  days, following the last dose of test article (3 days window).
  - b. For the CE-PTE population:
    - i. The Overall Clinical Response (based on the investigator's assessment) at the PTE Visit is not Indeterminate (see Table 5).

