    - ii. The PTE Visit occurred Day 21 (± 2 days), unless the subject was considered to be a Clinical Failure based on the investigator's assessment at the EOT visit.
  - c. For the CE-FFU population:
    - i. The overall Clinical Response (based on the investigator's assessment) at the Final Follow-up (FFU) Visit is not Indeterminate.
    - ii. The FFU Visit occurred on Day 28 ( $\pm$  2 days) from the first dose of test article), unless the subject was considered to be a Clinical Failure based on the investigator's assessment at the PTE visit.
- 3. Other Evaluability Criteria
  - a. Prior Antibiotic Therapy

Exclusion Criterion #2: Receipt of any dose of a potentially therapeutic antibacterial agent (with potential activity against uropathogens in the urinary tract) from 72 hours prior to randomization until the first dose of test article. [Note: Subjects who developed the current pyelonephritis while receiving prophylactic antibacterial

93 Version: 1.0 Status: Approved Approved Date: PTK0796-AP-17202 Statistical Analysis Plan

Omadacycline (PTK 0796)

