#### Table 3Scheduled Study Visits

Study Day is calculated relative to the first dose of test article (Day 1); there is no Day 0 – the day prior to the first dose of test article is Day -1. If no test article is taken, study day is calculated relative to the date of randomization.

For efficacy outcomes, the data collected at the EOT, PTE and FFU visits, regardless of when these occur will be utilized in the analysis in the ITT and micro-ITT population. The CE and ME populations exclusions due to windowing are outlined in Sections 4.4 and 4.5.

For each safety outcome and UTISA data, analyses will utilize assessments occurring during the scheduled visit windows (provided in Table 3). Thus, if a subject has a visit outside the scheduled visit window, for example, a PTE Visit occurred 20 days after the subject's first investigational product dose, the assessment will not be summarized with the PTE Visit but will be considered an unscheduled assessment. If a subject does not have an assessment at a scheduled visit and an unscheduled assessment was taken within the window for the time point (for example, 21 days ( $\pm$  2 days) after the subject's first day of therapy for PTE), these assessments will be summarized in the by time point analyses. If more than one measurement is

93 Version: 1.0 Status: Approved Approved Date: PTK0796-AP-17202 Statistical Analysis Plan

Omadacycline (PTK 0796)

PTK0796-AP-17202 Statistical Analysis Plan

taken during the visit window, the value taken on the scheduled visit will be utilized or if no scheduled visit was done, the first (earliest) measurement in the visit window will be used. If more than one measurement is taken on the same day, the assessment closest to the start of the dose will be used for on treatment values and the last measurement on the day will be used for post-treatment values. For worst overall post-baseline analyses, all assessments including those obtained from unscheduled visits will be included.

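### SAP 7.1.1.3 lets an out-of-window FFU visit make the EOT response Indeterminate; read literally or as a slip for FFU, this contradicts SAP 5.4

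*SAP*

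**What the plan says.** The sentence at issue closes the definition of Indeterminate in SAP 7.1.1.3, the section on clinical response at FFU: "If FFU visit assessment is not within the visit window the EOT response is defined as indeterminate". It is not limited to any analysis population.

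Four other places bear on it.

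- **SAP 5.4 (text below Table 3).** For efficacy, the data from the EOT, PTE and FFU visits, "regardless of when these occur will be utilized in the analysis in the ITT and micro-ITT population". The same section leaves window exclusions to the CE and ME populations, and applies windows to safety outcomes and symptom data.
- **SAP 7.1.1.1.** An EOT response is Indeterminate for one reason only: "EOT visit not completed".
- **SAP 4.4.** CE-FFU already carries a timing criterion: "The FFU Visit occurred on Day 28", with a tolerance of 2 days either way and an exemption for subjects who had failed at PTE.
- **Protocol 8.8.1.3.** FFU is Indeterminate when "Final Follow-up visit not completed". There is no window clause.

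The EOT response also feeds the next visit. Overall clinical response at PTE "is determined as follows (Table 5) from the investigator's assessments at the EOT and PTE Visits". In ITT and micro-ITT the success rate is divided by "of subjects with Clinical Success + # of subjects with Clinical Failure + # of subjects with Indeterminate response", so an Indeterminate counts as a non-success.

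**The concern.** For ITT and micro-ITT, SAP 5.4 and SAP 7.1.1.3 give opposite instructions for the same subject. SAP Section 1 ranks the SAP above the protocol, but that cannot settle a conflict between two sentences of the SAP.

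The wording also leaves open which response is recoded. Taken as written, a scheduling deviation around Day 28 erases an EOT outcome recorded weeks earlier, and the PTE outcome changes with it. Taken as a slip, with EOT written for FFU, the rule discards completed FFU assessments.

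Two programmers could therefore produce different clinical response tables from one database. This affects planned output: SAP 7.2.1 repeats the PTE analysis, with its credible intervals and posterior probability of non-inferiority, at EOT and FFU. SAP Table 12 says the efficacy results are meant to inform dose selection for a possible Phase 3 programme.

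**Working it through.** The plan states no figure on this point to reproduce. The check compares the rules, traces each reading through the SAP's own tables, and then sizes the effect under stated assumptions.

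**1. The rules side by side (ITT and micro-ITT)**

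| Situation | SAP 5.4, 7.1.1.1 and protocol 8.8.1.3 | SAP 7.1.1.3, literal | SAP 7.1.1.3, slip for FFU |
|---|---|---|---|
| EOT completed, FFU outside Days 26 to 30 | EOT outcome stands | EOT becomes Indeterminate | EOT outcome stands |
| FFU completed outside Days 26 to 30 | FFU outcome is used | FFU assessment kept, but combined with a changed PTE result | FFU becomes Indeterminate |

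Neither reading agrees with SAP 5.4.

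**2. Literal reading through SAP Table 5**

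Setting EOT to Indeterminate changes 3 of the 9 rows:

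| EOT / PTE | Overall PTE response in Table 5 | After recoding EOT |
|---|---|---|
| Success / Success | Success | Indeterminate |
| Failure / Success | Failure | Indeterminate |
| Failure / Indeterminate | Failure | Indeterminate |

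Only the first row moves the ITT success rate at PTE. The other two replace a Failure with Indeterminate, against the worst-case principle stated in SAP 7.1.1.2. All three also leave CE-PTE, which requires that the overall clinical response "at the PTE Visit is not Indeterminate (see Table 5"). The recoded EOT response likewise removes subjects from CE-EOT.

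**3. Slip reading through SAP Table 6**

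Setting FFU to Indeterminate changes 5 of the 12 rows, and all five become Indeterminate:

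- PTE Success with Clinical Cure, Clinical Failure or Relapse;
- PTE Indeterminate with Clinical Failure or Relapse.

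Only the cure row moves the success rate. The other four change category, since they are non-successes either way. Relapse is nevertheless a main finding of this visit. Appendix 1 of the protocol asks a subject who mentions recurrence by telephone to attend as soon as possible, and that visit could fall after Day 30.

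**4. Effect on the success rate**

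From the documents: about 200 subjects over 5 arms at equal allocation, 200/5 = 40 per arm, so each recoded success costs 1/40 = 2.5 points. Assumed, because the documents do not give them: out-of-window share *w* of 5%, 10% or 15%; PTE clinical success of 75%; cure share at FFU among PTE successes of 90%, 95% or 100%.

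- Literal reading, PTE rate = 0.75 × (1 − *w*).
- Slip reading, FFU rate = 0.75 × cure share × (1 − *w*).

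| Reading | No recoding | *w* = 5% | *w* = 10% | *w* = 15% |
|---|---|---|---|---|
| Literal, PTE | 75% | 71.3% | 67.5% | 63.8% |
| Slip, FFU, cure share 100% | 75% | 71.3% | 67.5% | 63.8% |
| Slip, FFU, cure share 95% | 71.3% | 67.7% | 64.1% | 60.6% |
| Slip, FFU, cure share 90% | 67.5% | 64.1% | 60.8% | 57.4% |

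**5. Effect on the posterior probability (literal reading, PTE)**

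SAP 7.2.1 uses binomial counts with Beta(0.5, 0.5) priors, so each rate has posterior Beta(0.5 + y, 0.5 + n − y). The quantity computed is the chance that P(pOMC − pLEV > −0.1 | data) is at least 0.70, by exact enumeration over both binomials with n = 40 per arm. The 0.70 value is the sample-size target for the composite endpoint (SAP 3.1), used here only as a yardstick.

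| Recoded share, OMC / LEV | Rates, OMC / LEV | Chance of reaching 0.70 |
|---|---|---|
| None | 0.75 / 0.75 | 0.708 |
| 5% / 5% | 0.7125 / 0.7125 | 0.673 |
| 10% / 10% | 0.675 / 0.675 | 0.650 |
| 15% / 15% | 0.6375 / 0.6375 | 0.639 |
| 10% / 5% | 0.675 / 0.7125 | 0.520 |
| 15% / 5% | 0.6375 / 0.7125 | 0.371 |

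**The case against.** The best defence is that nobody would programme the literal reading. The sentence sits in the FFU section, inside the definition of an Indeterminate FFU outcome, and SAP 7.1.1.1 defines Indeterminate at EOT with no reference to FFU. If the word is a slip, EOT and PTE results are safe, CE-FFU is windowed anyway, and what remains is FFU clinical response in ITT and micro-ITT. That is a later-visit repeat of an analysis in which all efficacy endpoints are exploratory and inference is nominal.

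The EOT-failure rows can also be played down. SAP 7.1.1.2 has the investigator assess PTE response only in subjects who were a success or Indeterminate at EOT, and 7.1.1.3 has FFU response assessed only in PTE successes. EOT failures would therefore not ordinarily have an FFU response to fall out of window.

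Finally, the sizes rest on assumed rates. The two largest falls need out-of-window shares that differ by arm, for which a double-blind trial gives no obvious reason, and SAP 7.2.1 attaches no decision threshold to clinical response.

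Much of this stands as to weight. The slip is the more likely intent, and the unequal-loss figures are illustrations, not forecasts. EOT failures are a minor route, though not a closed one: Tables 5 and 6 list such rows, and protocol 9.4.2 schedules the FFU assessment for prematurely withdrawn subjects who have not withdrawn consent. None of it removes the contradiction, because the slip reading conflicts with SAP 5.4 too.

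**Conclusion.** The concern holds. SAP 7.1.1.3 conflicts with SAP 5.4 in ITT and micro-ITT under either reading, and nothing else in the two documents resolves it. The literal reading also conflicts with SAP 7.1.1.1. The slip reading adds a window condition absent from protocol 8.8.1.3, and SAP Table 12 does not list it as a change.

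On the probable reading the consequence is confined to FFU. With a 95% cure share, the ITT success rate loses about 3.6 to 10.7 points (71.3% − 67.7% to 71.3% − 60.6%), and some relapses and failures are relabelled Indeterminate. On the literal reading the PTE clinical success rate is affected as well, by about 3.8 to 11.3 points (75% × 5% to 75% × 15%). Equal loss across arms lowers the chance of meeting the 0.70 yardstick only modestly, from 0.71 to between 0.67 and 0.64; larger falls require unequal loss.

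All these sizes depend on the assumed out-of-window, success and cure rates. The contradiction does not. It should be corrected as a faulty derivation rule; it does not threaten a confirmatory conclusion.

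**What to change.** Delete the sentence from SAP 7.1.1.3. Alternatively, change it to refer to the FFU response and restrict it to CE-FFU, where SAP 4.4 already imposes Day 28 ± 2. Either change brings 7.1.1.1, 7.1.1.3 and 5.4 into agreement. Table 5 should stay as it is, as the pre-specified worst-case rule.

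If the sponsor does want a window rule for FFU in ITT or micro-ITT, SAP 5.4 should be amended to say so, and the rule listed in Table 12 as a departure from protocol 8.8.1.3.

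The cost is one sentence of SAP text and one line of derivation code, with no new data. SAP 3.5 provides for amendments approved before database lock, and the change belongs there; the documents do not show whether lock has taken place.
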